The total modified RSI score at 8 weeks will be averaged for each group (amitriptyline vs. placebo) and differences compared between the treatment and placebo arms using analysis of covariance adjusting for baseline severity scale at an overall two-sided 0.05 level of significance across the interim and final analysis (a two-sided significance level

of 0.00306 at the interim and 0.049 at the final analysis). A Wilcoxon Rank Sum test will be used in the case that the data is found to have a non-normal distribution.

A secondary outcome will be improvement in overall symptoms (yes/no), as subjectively assessed by patients. The post treatment survey will ask both the patient and the principal investigator whether they thought the subject was on amitriptyline or placebo.

Additional secondary outcomes will be whether there are changes in scores from baseline on the Voice Handicap Index-10 after treatment [Rosen et. al. Development and Validation of the Voice Handicap Index-10. *The Laryngoscope*. 2004; 114: 1549-1556] and change in score from baseline on the Cough Severity Index (CSI).[Shembel AC et al.. Development and validation of the cough severity index: a severity index for chronic cough related to the upper airway. *Laryngoscope*. 2013;123(8):1931-6.] The VHI-10 is a 10-question scale that addresses effects on quality of life from voice disorders while the CSI is a 10-item likert scale that assesses cough symptoms. Furthermore, we will determine whether the severity of each symptom within the modified RSI has improved after treatment. This will account for questions that may be less relevant to laryngitis overall (and more specific to reflux).

Frequencies of AEs for both groups of patients and the rate of discontinuing treatment will be recorded.

The study will be stopped if any patient is permanently disabled, seriously injured, or dies in a manner that could be consistent with the drug usage. The study will be continued if said patient(s) were taking the placebo or the event is demonstrably unrelated to the subject's participation in the trial.

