An independent monitor within the otolaryngology department who is not associated with study recruitment or data analysis will also review adverse events for all subjects. The independent monitor will submit a report to the PI, who will then review these events and submit a report to the IRB. Also, if there is a concerning event or group of events, the PI will bring these to the attention of the independent monitor as they occur.

A report will be submitted to the IRB and the PI by the independent monitor at the intervals described in safety monitoring section (see section on Safety monitoring/reporting for more detail).

Analysis (efficacy and safety)

We will be using the 8 week post-treatment 11-point modified RSI score as our primary outcome. Treatments will be compared using analysis of covariance adjusting for the baseline value using a two-sided 0.05 level of significance.

We thus used the RSI to calculate our sample size. The average starting RSI for subjects with a similar type of laryngitis to what we are studying is 20.9. After treatment, the average was 12.8 (Belfasky et. al. 2002). We estimated a 20% improvement for the

placebo group, using the estimate for continuous indicators from Hróbjartsson et. al. meta-analysis of placebo effects. Thus, we predicted the final mean RSI for the placebo patients to be 16.72. The difference between the means is thus assumed to be 3.92. Dividing this mean difference by the anticipated standard deviation (10.0, using the value from Belfasky et. al. for the final RSI value post-treatment) gives an anticipated standardized effect size of 0.392. Using this for the calculation for a-priori sample size calculations (using two-sided $p < 0.05$ and a desired power level of 0.8) gives a needed sample size of 208.

In prior pilot study data, mean difference in RSI scores was +13 (increase in score post treatment) for the amitriptyline group and +16.4 in the placebo group, with standard deviations of 7.8 and 12.1, respectively. The p-value used to determine significance was 0.5 for a two-tailed unpaired t-test.

Currently, funding is available for 100 subjects to complete this study, not including subjects who completed treatment in the prior pilot study. With a dropout rate of 30%, we expect to enroll 130 subjects in order for 100 to complete treatment. With a standard deviation of 10 as per prior assumptions, we would be able to detect a mean difference of 6 by one-tailed ANOVA analysis.

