When 25 subjects in each arm (placebo and amitriptyline) have completed the study and follow-up (i.e. at least 50 subjects total), a blinded interim analysis will be performed, and conditional power for detecting a significant treatment effect by the planned end of the study (100 subjects) will be determined. If this conditional power is between 50 and 80%, the sample size will be recalculated to achieve 80% conditional power following the algorithm of Chen and DeMets (2004). Otherwise, the study will continue until 50 subjects in each arm have completed treatment.

For data analysis, we will be performing both per-protocol and multiple imputation approach analyses. Multiple imputation using the linear regression approach will be used to impute missing data, for subjects who do not complete treatment. Intention-to-treat analysis is not possible, since our outcomes are determined by the 8 week post-treatment survey, and there are no intermediate data points with regards to treatment efficacy outcomes (ie, subjects who drop out will not have any outcomes recorded).

The primary outcome measure will be the pre- and post- treatment difference in scores on the Reflux Symptom Index (RSI), with two additional questions added to assess for symptoms that may be more specific to chronic laryngeal neuropathy.

The RSI is a validated questionnaire consisting of 9 statements to be ranked 0-5. We have added two additional symptoms to be assessed to the RSI, "throat pain or burning" and "pain with swallowing", which we believe may also be relevant to chronic laryngeal neuropathy.

The modified RSI score will be averaged for each group (amitriptyline vs. placebo), and since it is a nearly continuous variable (with an expected normal distribution) and we will

be comparing the mean of the change rather than categorizing the treatment into responder and non-responders, we will also analyze it using an Analysis of Covariance or Wilcoxon Rank Sum test if determined to have a non-normal distribution.

For the modified RSI, we will also conduct a secondary analysis looking at change in severity of each symptom individually. This will account for questions that may be less relevant to laryngitis overall (and more specific to reflux).

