Secondary outcome measures will be 1) subjective percent improvement from baseline to after 8 weeks of treatment, 2) subjective report of whether symptoms are better, worse, or same after treatment, and 3) the pre- and post- treatment mean difference in scores on the Voice Handicap Index-10 (VHI-10). 4) the pre- and post- treatment mean difference in scores on the Cough Severity Index.

The VHI-10 is a 10-question scale that addresses effects on quality of life from voice disorders. By asking respondents to score symptoms on the VHI-10 scale, we expect to gain additional data on the effects of amitriptyline on improvement in voice-related issues.

The Cough Severity Index is a 10-item likert scale. which is a validated questionnaire used to quantify a patient's symptoms associated with upper airway chronic cough, and will allow us to better understand the effect of the amitriptyline intervention for chronic cough.

Subjects

Inclusion Criteria:

1. Age 18 or older and able to consent for themselves
2. Structural pathology such as tumor previously ruled out using flexible laryngoscopy
3. Able to speak and read the English language
4. Failed a 2 month or longer trial of a proton pump inhibitor for the treatment of gastro-esophageal reflux
5. Women under 55 years of age who may become pregnant must have a negative pregnancy test and agree to barrier or hormonal methods of contraception during the study

Exclusion Criteria:

1. Active, untreated environmental allergies.
2. Smoking within past 5 years
3. Current upper respiratory infections
4. Use of narcotics (e.g. oxycodone, methadone) within the past week
5. History of amitriptyline use or other tricyclic antidepressants, pregabalin, gabapentin, baclofen, or other GABA analogues or inhibitors, for any medical conditions (not limited to chronic laryngitis) within the past 6 months
6. Use of any other monoamine oxidase inhibitors (MAOIs) other than amitriptyline

- within the past 4 weeks (selegiline, phenelzine, tranylcypromine, isocarboxazid, rasagiline, phenelzine sulfate, selegiline hydrochloride, rasagiline mesylate, tranylcypromine sulfate)
7. History of urinary retention
 8. History of an acute episode of a major depressive disorder within the past 12 months
 9. For women 18-55 years of age without history of menopause: currently nursing or pregnant, plans to become pregnant, or unwillingness to utilize contraception (barrier or hormonal methods)
 10. Currently participating in another clinical trial.

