of 50mg nightly is reached. If the dose is increased and results in side effects such as intolerable dry mouth or fatigue, the patient will be counseled to decrease the dose to the most recent one that was well tolerated. Each patient will be given a "diary" that will specify both the recommended dose escalation schedule and space for the patient to record on a daily basis the dose that was actually taken. All patients will be asked to bring back all remaining capsules at the end of the 8 week treatment period, or return remaining capsules via a prepaid mailer, to further corroborate the dosing diary. At the conclusion of the 8 weeks of treatment, the patients may discontinue the medication without any additional tapering. However, if they choose to start a new prescription of amitriptyline before conclusion of the entire study period, they will be counseled that they will need to re-titrate gradually increase the dosage as needed, at the prescribing clinician's discretion.

At the first study visit, if they meet eligibility criteria, he/she will be asked to complete a pre-treatment questionnaire, which will include the Voice Handicap Index-10 (VHI-10), Cough Severity Index, and a modified Reflux Symptom Index (RSI) scales to assess the baseline severity of symptoms. The RSI will be modified to assess two additional symptoms which are commonly seen with chronic laryngitis, "throat pain or burning" and "pain with swallowing". After these forms have been collected, coded data will be added to a secure database, and the original forms will be kept in a secure locked location. All information in the database will be input under the subject's assigned study number. A separate secure database will be kept correlating the subject's assigned study number to personal identifying information, such as contact information, which will be accessed only as needed to assess for trial safety and to contact subjects. Randomization data will be kept separately, accessible only to BMC Investigational Pharmacy Services (IPS) until study completion, except in case of emergency.

If the subject meets all inclusion criteria they will be assigned a randomization number and receive the assigned study drug according to the Treatment Assignment Table prepared by BMC IPS. The drug may be given to the subject in person or mailed to the subject's address.

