The treatment assignment will not be available to the clinical staff that will administer the study questionnaires and analyze resulting data while subjects are receiving the study drug or placebo, except in case of severe adverse side effect or other emergency requiring urgent unblinding. If emergency unblinding is required as noted by the PI or study staff, they will contact the IPS on-call personnel who will have access to the randomization table.

On Days 7, 14, 21, 28, 35, 42, 49, and 56 of the study the subject will be contacted by phone by a blinded study coordinator. The subject will be asked about side-effects and concerns, and confirm the dose they are taking that week. The study coordinator will relay any medical concerns to the primary investigator for consideration and follow-up, or to the nearest emergency department if the issue is too urgent to wait. The study staff will instruct the subject to remain at the same dose, increase the dose by 1 capsule or discontinue the study drug in accordance with the protocol. The subject will also be encouraged to contact the study coordinator both before and after the scheduled phone

calls and initial visits if they experience any adverse events or have additional concerns.

The subject will be instructed to discontinue taking all capsules after 8 weeks, regardless of the number of capsules remaining or any improvement experienced on the capsules. No tapering is required prior to stopping treatment.

At the time of enrollment, at the initial study visit, the subject will also be scheduled for an in-office follow-up 8 weeks after starting the capsules (as is standard of care for the treatment of chronic laryngitis). At this visit the subject will be asked to fill out a post-treatment questionnaire including a repeat modified RSI, CSI, VHI-10, and reported overall subjective percentage improvement from baseline. The latter will serve as a separate independent variable, given that neither the RSI, CSI, nor VHI-10 were specifically designed to evaluate chronic laryngeal neuropathy. Any questions the subject might have regarding the questionnaires are answered by the PI.

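### VHI-10, Cough Severity Index and single-symptom outcomes are defined only as changes, with no model or covariate; baseline-adjusted ANCOVA would be a free gain in precision

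*Combined protocol and SAP*

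**What the plan says.** The Analysis (efficacy and safety) section of the combined protocol and SAP gives the primary outcome, the modified RSI total, a model: "Treatments will be compared using analysis of covariance adjusting for the baseline value". Study Design says the same, with a Wilcoxon rank sum test if the data are non-normal.

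The secondary scales get a quantity and no model:

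- VHI-10: Study Design asks "whether there are changes in scores from baseline on the Voice Handicap Index-10 after treatment". The list of secondary outcomes in the analysis section calls it a pre- and post-treatment mean difference.
- CSI: the same list gives "the pre- and post- treatment mean difference in scores on the Cough Severity Index", and Study Design also defines it as a change from baseline.
- Single modified-RSI symptoms: the analysis section plans a secondary analysis of "change in severity of each symptom individually". Study Design asks whether the severity of each has improved after treatment.

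No test, covariate or between-arm contrast is written for any of these.

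The data for an adjusted analysis will exist. Study Procedures describes the form completed before treatment, "which will include the Voice Handicap Index-10 (VHI-10), Cough Severity Index, and a modified Reflux Symptom Index (RSI) scales to assess the baseline severity", and the 8-week questionnaire contains "a repeat modified RSI, CSI, VHI-10".

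**The concern.** An analyst who follows the secondary-outcome text as written would subtract baseline from the 8-week score and compare the arms' mean differences. The plan has a precedent for this: it reports the pilot's RSI differences by arm with an unpaired t-test. A raw change score fixes the weight on baseline at 1, whatever the data show. ANCOVA estimates that weight, so it removes more noise and corrects a chance baseline imbalance by the right amount.

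The trial has little precision to spare. It is funded for 100 completers against its own calculated need of 208. Leaving the method open also allows a choice between adjusted and unadjusted results once the data have been seen.

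**Working it through.** **Inputs from the documents.** Planned completers are 50 per arm, with 1:1 allocation and a two-sided 0.05 level. The RSI assumptions are a difference of 3.92, an SD of 10 and hence a standardized effect of 0.392. No SD, pre-post correlation (rho) or expected effect is given for VHI-10, CSI or the single items, so rho is assumed over a range.

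**The plan's own figure.** A two-sample t-test with effect size 0.392, two-sided 0.05 and 80% power needs 103.1 per arm, rounded up to 104, or 208 in total. This matches the stated 208. (The normal approximation gives 103 per arm, 206 in total.) That calculation takes no credit for baseline adjustment and concerns the RSI only.

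**Variance per subject.** Let s be the SD, assumed equal at both visits.

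- Raw change: 2s²(1 − rho)
- ANCOVA: s²(1 − rho²)
- Ratio, ANCOVA to raw change: (1 − rho²) / [2(1 − rho)] = (1 + rho)/2

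The standard error ratio is the square root of this. The number of completers that a raw-change analysis needs to match ANCOVA with 100 is 100 × 2/(1 + rho).

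| Assumed rho | Variance, raw change (s²) | Variance, ANCOVA (s²) | Ratio | SE smaller by | Completers needed with raw change |
|---|---|---|---|---|---|
| 0.3 | 1.40 | 0.91 | 0.65 | 19% | 154 |
| 0.5 | 1.00 | 0.75 | 0.75 | 13% | 133 |
| 0.7 | 0.60 | 0.51 | 0.85 | 8% | 118 |
| 0.9 | 0.20 | 0.19 | 0.95 | 3% | 105 |

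**Power, as an illustration.** For an assumed true difference of 0.5 SD of the 8-week score and 50 per arm, a two-sample t-test calculation uses effect size 0.5 divided by the square root of the variance above. Raw change versus ANCOVA gives:

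- rho 0.3: 0.55 versus 0.74
- rho 0.5: 0.70 versus 0.82
- rho 0.7: 0.89 versus 0.93

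At rho 0.9 both exceed 0.99.

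**Change or final score as the outcome.** In one simulated data set of 50 per arm, the 8-week score regressed on arm and baseline gave a treatment estimate of −3.62 (SE 1.745). The change regressed on arm and baseline gave the same estimate and SE. The change regressed on arm alone gave SE 1.956. The loss therefore comes from leaving out the covariate, not from calling the outcome a change.

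**Unequal variances.** If the follow-up SD is k times the baseline SD, the ratio becomes k²(1 − rho²) / (1 + k² − 2·rho·k). At rho 0.7:

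- k = 1/0.7 = 1.43: 1.041/1.041 = 1.00, so no gain
- k = 1: 0.51/0.60 = 0.85
- k = 0.7: 0.250/0.510 = 0.49, a larger gain

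In large samples ANCOVA is never the less precise of the two, apart from one degree of freedom, but the gain depends on k as well as rho.

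**The case against.** The strongest reply is that the plan never says these scales will be analysed without adjustment. The text in question is a list of outcome measures. The same section describes the primary outcome in nearly the same terms, as a pre- to post-treatment difference, speaks of comparing mean changes, and still names ANCOVA. Change wording in this plan therefore does not by itself mean an unadjusted analysis. This stands, and it makes the loss conditional. It does not close the gap, because the ANCOVA sentences attach to the modified RSI and nothing extends them to the other measures.

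A reader might also infer that a within-arm before-after test is intended, since the Study Design wording for VHI-10 names no comparator. Such a test would credit placebo response to the drug, and the plan itself expects a 20% improvement on placebo. The documents do not support that reading: the design is randomized and placebo-controlled, the hypothesis is superiority to placebo, and no within-arm test is written anywhere.

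Three further limits are fair. The size rests on assumed correlations and equal variances. An unadjusted between-arm comparison of changes would still be unbiased under randomization. The power figures treat the outcomes as continuous, so they do not carry over to single items scored 0-5, for which plain ANCOVA may not be suitable.

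**Conclusion.** The point holds as a free improvement to the secondary analyses. The documents do not establish that raw change scores will be used, but that is what the secondary-outcome text yields if followed literally, and no adjusted method is written for these measures. If raw change were used, ANCOVA would cut the variance by 35%, 25%, 15% or 5% at assumed correlations of 0.3, 0.5, 0.7 or 0.9, given equal variances at the two visits. None of these inputs can be fixed from the documents for VHI-10 or CSI. The primary analysis is not affected, and neither are the percent-improvement and better/worse/same outcomes, which have no baseline score.

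**What to change.** Add to the analysis section:

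- VHI-10 and CSI will be compared between arms by ANCOVA adjusted for that measure's own baseline, and reported as an adjusted difference with 95% CI. The outcome may be the 8-week score or the change, since both give the same treatment estimate.
- Each modified-RSI symptom will be compared between arms with adjustment for its own baseline. A rank-based or ordinal method will be used where the distribution is non-normal, in line with the rule that the plan already has for the total score.
- For all these measures the efficacy contrast is between arms.

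The cost is a few sentences, settled before unblinding. No new data, visits or subjects are needed, and the model uses one extra degree of freedom per analysis.

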The target of our study is to have 100 subjects complete the study, excluding prior pilot study data. We will run a blinded interim analysis on the primary endpoint when 25 subjects in each arm have completed treatment and follow-up, and a conditional power for detecting a significant treatment effect by the planned end of the study (100 subjects) will be determined. If this conditional power is between 50 and 80%, the sample size will be recalculated to achieve 80% conditional power following the algorithm of Chen and DeMets (2004). Otherwise, the study will continue until 100 patients have completed treatment.

Based on prior pilot study data, we anticipate the study dropout rate to be approximately 30%, from time of initial enrollment to completion of the post-treatment survey. During the prior pilot study, the dropout rate was 50% initially, and dropped to 30% during the last 8 months of enrollment, until the study was closed. Dropout rate was the same in each arm, with 5 subjects in each arm dropping out after starting treatment. Only three subjects cited adverse events (AEs) as a reason for drop out; two subjects on placebo complained of headache and dry mouth, respectively, and one subject on amitriptyline complained of sedation.

Thus, we anticipate a dropout rate during treatment of 30%, and anticipate having to enroll at least 75 subjects in order for 25 patients in each arm to complete the study by the interim analysis.

The physician may elect to discontinue study drug due to serious adverse events (SAEs) or unintended pregnancy. If a subject withdraws from treatment due to adverse events, we will ask that they continue coming in for follow-up visits and finish the remaining parts of the visits off the study drug.

The primary endpoint of the trial will be the total modified RSI at 8 weeks. The Reflux Symptom Index (RSI) has been validated by Belfasky et. al. [Belafsky PC, Postma GN, Koufman JA. Validity and reliability of the reflux symptom index (RSI). *Journal of Voice*. 2002;16:274-277]. The RSI is a questionnaire consisting of 9 statements to be ranked 0-5. We have added two additional symptoms to be assessed with the RSI, "throat pain or burning" and "pain with swallowing", which we believe are also relevant to chronic laryngeal neuropathy.

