The PI of the study will have overall responsibility for the monitoring plan. Blinded study coordinators will contact each subject by phone once per week during the study period to monitor for adverse events. Adverse events will be documented and reported to the PI on a weekly basis and classified as per "adverse event definitions" outlined in the supplement section below. Any event that is severe and/or serious will be reported to the PI immediately. If the event is determined to meet the criteria for Unanticipated Problem (UP) it will be reported to the IRB within 2 business days.

The study will be stopped if any patient is permanently disabled, seriously injured, or dies in a manner that could be consistent with the drug usage. The study will be continued if said patient(s) were taking the placebo or the event is demonstrably unrelated to the

subject's participation in the trial.

An independent monitor within the otolaryngology department who is not associated with study recruitment or data analysis will also review adverse events (see appendix for definitions) for all subjects after every 10th subject has completed 8 weeks of treatment. [name] has agreed to act as this independent monitor. He is not directly supervised by the PI, [name]. His salary is not determined or affected by [name]. The independent monitor will submit a report to the PI, who will then review these events and submit a report to the IRB. Also, if there is a concerning event or group of events, the PI will bring these to the attention of the independent monitor as they occur, within 2 business days, regardless of whether they are thought to be related to treatment or not.

Additionally, reporting to the IRB will be expedited (within 2 business days) for any event that is unexpected, possibly related to treatment and causes risk to subjects or others, or is serious.

We will assess and document all adverse events and will report any adverse event that meets the definition of unanticipated problem, as defined in the Boston Medical Center Data Safety and Monitoring Plan (DSMP).

A report will be submitted to the IRB and the PI by the independent monitor at the above intervals.

Upon enrollment, subjects will be provided with an emergency contact card with a short description of the study drug used and contact information for Investigational Pharmacy services, in case of emergency.

Funding

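### The independent monitor's scheduled safety review is triggered only by treatment completers, so its spacing lengthens, modestly, as dropout rises

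*Combined protocol and SAP*

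**What the plan says.** **Trigger.** Under Safety monitoring/reporting, the independent monitor reviews adverse events "for all subjects after every 10th subject has completed 8 weeks of treatment". The same section adds: "A report will be submitted to the IRB and the PI by the independent monitor at the above intervals". Study Design gives no separate schedule and refers back: "A report will be submitted to the IRB and the PI by the independent monitor at the intervals described in safety monitoring section". No other timing for the scheduled review appears.

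**Early stoppers.** Study Design asks subjects who withdraw from treatment because of adverse events to remain in follow-up without the drug. They stay under observation but have not completed 8 weeks of treatment.

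**Dropout.** Study Design describes the 30% in two ways. It is first counted from enrolment to the post-treatment survey. It then becomes an on-treatment rate: "we anticipate a dropout rate during treatment of 30%, and anticipate having to enroll at least 75 subjects". For the pilot, "the dropout rate was 50% initially, and dropped to 30% during the last 8 months of enrollment", "with 5 subjects in each arm dropping out after starting treatment". Three pilot subjects gave adverse events as the reason, two on placebo and one on amitriptyline. Analysis (efficacy and safety) plans 130 enrolled for 100 completers.

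**Other safety routes (Safety monitoring/reporting).**
- Coordinators telephone every subject weekly, and adverse events go to the PI weekly.
- Severe or serious events go to the PI at once.
- Serious events, and unexpected, possibly related events that pose risk, go to the IRB within 2 business days.
- The PI takes a concerning event, or group of events, to the monitor within 2 business days.

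**The concern.** The population reviewed and the population that triggers the review differ. Someone who stops at week 2 because of sedation contributes data to the next review but does nothing to bring it closer. The higher the early stopping, the more subjects are started between scheduled reviews, which is the wrong direction for a safety schedule.

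At stake is the timing of the only scheduled independent look at non-serious events and withdrawals as they build up. Study Procedures expects side effects to appear within the first 4 weeks, so an early stopper's tolerability information usually exists well before the completer count reaches its next multiple of ten.

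**Working it through.** The plan states no figure for review spacing beyond every tenth completer, so there is none to reproduce.

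**Spacing.** Let d be the proportion of subjects started who do not complete 8 weeks of treatment. Subjects per review = 10/(1 − d).

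| Source of d | d | Subjects per review |
|---|---|---|
| No dropout | 0 | 10 |
| 130 enrolled for 100 completers | 1 − 100/130 = 23.1% | 10 × 130/100 = 13 |
| Stated 30%, all on treatment | 30% | 10/0.70 = 14.3 |
| Pilot's early rate, if it were all on treatment | 50% | 10/0.50 = 20 |

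The interim planning figure of 75 enrolled for 50 completers would give 10 × 75/50 = 15. But 30% dropout needs only 50/0.70 = 71.4, that is 72 subjects, so I read 75 as a rounded-up recruitment number.

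The 13 and 14.3 treat every non-completer as someone who started drug and stopped. Enrolled subjects who never took drug are not exposed. Subjects who finished 8 weeks but missed the survey do advance the count. Either group makes the true spacing in treated subjects shorter.

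**Time to first review.** The documents give no accrual rate, so r (starts per week) is assumed. Weeks to first review ≈ 10/[r(1 − d)] + 8.

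| r (assumed) | d = 0 | d = 23.1% | d = 30% |
|---|---|---|---|
| 0.5 | 28.0 | 34.0 | 36.6 |
| 1 | 18.0 | 21.0 | 22.3 |
| 2 | 13.0 | 14.5 | 15.1 |

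At 30% the first review is about 2 to 9 weeks later than with no dropout.

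**Part due to side effects.** Assume the three pilot subjects who cited adverse events were among the 10 (5 per arm) who dropped out after starting treatment. Then 0.30 × 3/10 = 9% stop for adverse events, and spacing from that cause alone is 10/0.91 = 11.0. The Drug Profile section reports that under 10% of over 50 clinic patients stopped for side effects, which gives at most 10/0.90 = 11.1.

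**Number of reviews.** The trial runs to 100 completers, so there are 100/10 = 10 scheduled reviews whatever the dropout. Dropout stretches the reviews over more subjects and does not remove any.

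**The case against.** The strongest case against is that little is left uncovered. Weekly calls pick up events, serious events move at once, and the 2-business-day route to the monitor expressly includes groups of events, related or not, so a cluster of non-serious complaints can reach the monitor early. Every review covers all subjects, so stoppers' events are seen. Nothing in the text contradicts itself, and every tenth completer is already frequent.

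Most of this stands, and it limits the point to timing. It does not remove it:
- The route to the monitor opens only when the PI judges something concerning, and the PI has overall responsibility for the monitoring plan.
- The expedited IRB route needs an event to be serious, or unexpected, possibly related and risky. Adverse Event Definitions makes listed effects expected, and the Drug Profile lists sedation, dizziness and dry mouth. Non-serious sedation that leads subjects to quit need not trigger it.
- Routine events go weekly to the PI and not to the monitor.

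A reader might also infer several stronger things that the documents do not support:
- *That the interval doubles to 20.* The 50% is never called an on-treatment rate, and it follows a definition that runs from enrolment to the survey.
- *That 43 treated subjects never move the count* (100/0.70 = 143). The plan's own figure is 130 enrolled, so 30 non-completers, and some of those may never take drug.
- *That poor tolerability is the main cause of delay.* Only three pilot subjects cited adverse events, and two of them were on placebo.
- *That the PI is the only early route to independent eyes.* That is true for the monitor but not for the IRB.

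**Conclusion.** The point holds as a minor design weakness. The scheduled review is tied to completers with no backstop, so its spacing grows with early stopping. It is 13 subjects per review on the plan's enrolment figures and at most about 14.3 if all of the stated 30% occurs on treatment, against 10 with no dropout. Twenty is only an illustrative upper bound.

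The consequence is a later scheduled independent look at accumulating non-serious events and withdrawals, most of it caused by dropout for other reasons. The text does not support reading this as lost safety data, fewer reviews, or a failure of serious-event reporting. The size depends on how much of the dropout occurs between first dose and week 8, which the documents do not separate, and the delay in weeks depends on an accrual rate they do not give.

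**What to change.** In Safety monitoring/reporting, count each subject once, on completing 8 weeks of treatment or on permanently stopping study drug, whichever comes first, and hold the review after every tenth subject so counted. The cross-reference in Study Design then needs no edit. Spacing becomes 10 subjects whose treatment has ended, whatever the dropout.

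The cost is one sentence and a few more reports from the monitor already appointed: 130/10 = 13 on the plan's enrolment, or 143/10 ≈ 14 if 30% drop out on treatment, against 10 now. It would be fewer if some non-completers never start drug. Dosing, stopping rules, blinding and the efficacy analysis are unaffected.
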